Document date: 07/18/2023

Impacts of mitochondrial-targeted antioxidant on leg function, leg blood flow and skeletal muscle mitochondrial function in peripheral artery disease patients: full study protocol and statistical analysis plan

NCT# 03506633

Study protocol

Participants

Patients with PAD (n = 13, 7 males and 6 females) were recruited for study participation. Disease staging, claudication history, and ankle-brachial index of <0.90 were determined by both self-report and by physician diagnosis, and all participants were classified as Fontaine stage IIa and IIb (16). Participants were also required to have a stable BP, lipid, and/or diabetes regimen for \geq 6 wk prior to participation, and all females were postmenopausal (no menses for \geq 12 consecutive months). Participants were excluded from the study if they had a history of pain at rest (Fontaine stage III) and/or tissue loss due to PAD (Fontaine stage IV), limited walking capacity due to conditions other than PAD, or renal disease. Participants were also asked to track what they consumed the day before their first visit so they could consume the same foods prior to their second visit. In addition, participants were requested to not alter their digtary habits during the 2 wk washout period. All procedures were performed according with the protocols approved by the Institutional Review Board and performed in accordance with the Declaration of Helsinki. All participants provided written, informed consent prior to beginning the study. This study was registered with https://clinicaltrials.gov/ (NCT03506633).

Design

This study used a randomized, double-blinded, placebo-controlled, crossover design with a washout period of 14 days between the 2 study visits (**Fig. 1**). Participants were randomly assigned to receive either 80 mg of MitoQ or placebo. In a previous study, MitoQ showed pharmacokinetic behavior at doses of 80 mg (1mg/1kg), resulting in plasma maximal concentration of 33.15 ng.ml, which is safe for humans. Additionally, administration of 20 mg/1kg of mitoQ was shown to have no toxicity in previous research. The dose in this study was considerably lower than this amount. These findings led us to believe the recommended

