80 mg dose is ideal for this study. The PL consisted of tapioca powder capsules that possessed no nitrate or antioxidant properties. Participants were informed that we were researching the effects of commercially available juice and pills on their vascular function and walking capacity; therefore, they were not aware that the capsules were PL. All assessments were performed after an overnight fast and at the same time of day (9:00 AM \pm 1 h). Anthropometric measurements were obtained upon arrival at both visits. Following anthropometrics, baseline experimental measurements were conducted, after which the MitoQ supplement or PL were consumed. All experimental measurements were repeated ~ 1 h following ingestion. All data analyses were performed in a blinded manner.

Anthropometrics

Anthropometric measurements included height, body mass, and body composition. Height was measured using a stadiometer (nearest 0.5 cm). Body mass was measured using a standard scale (nearest 0.1 kg), and body mass index was calculated by taking the body mass divided by height squared (kg/m²). Body fat percentage was assessed using bioelectrical impedance analysis in duplicate to the nearest 0.1% (HBF – 306C, Omron Healthcare, Lake Forest, IL), and the average of the 2 measures was recorded as the body fat percentage.

Resting heart rate and blood pressure

Participants sat for 15 min in a quiet and temperature-controlled room. Resting heart rate and BP were assessed in duplicate using an automated sphygmomanometer (HEM – FL 31, Omron Healthcare, Lake Forest, IL). The two measurements were taken with 5 min separating each measurement, and the average of the 2 was recorded as the resting heart rate and BP.

Endothelial function

Endothelial function was assessed using brachial artery flow-mediated dilation (FMD) and popliteal artery FMD using a Doppler ultrasound (Terason uSmart 3300, Terason Division Teratech Corporation, Burlington, MA), rapid inflation cuff system (E20 Rapid Cuff and cuff model SC5, D.E. Hokanson, Bellevue, WA), and a 3-lead electrocardiogram system (7700 Series

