Trigger Monitor, IvyBiomedical Systems Inc., Branford, CT) as previously described (22). Briefly, for both brachial and popliteal assessments, the rapid inflation cuff was placed just distal to the antecubital fossa and just distal to the popliteal fossa, respectively (22). For both assessments, resting arterial diameter was recorded with the ultrasound probe ~ 1-2 cm proximal to the rapid-inflation cuff for 5 min (22). The cuff was inflated to a pressure of 250 mmHg after baseline diameter was obtained and remained inflated for 5 min (22). The cuff was then deflated and the reactive hyperemic arterial response was recorded continuously on R-wave trigger for 5 min (22). Data were analyzed using an image capturing and automated edge-detection software (Vascular Imager, Vascular Research Tools 6, Medical Imaging Applications, Coralville, IA) as previously described (22).

Walking capacity and skeletal muscle oxygen utilization capacity

Maximal walking capacity was assessed on a standard treadmill (Lode, B.V, Groningen, The Netherlands) using the modified Gardner protocol (22, 24). Participants were asked to notify the test administrators about their onset of claudication (the exact moment their leg pain starts) and to walk as long as they could tolerate even if the claudication persisted (maximal walking time and distance). The test was ended once patients could not tolerate their symptoms (i.e., severe claudication).

Gastrocnemius oxygen utilization capacity was measured with a portable near-infrared spectroscopy (NIRS) unit (Artinis PortaMon, Einsteinweg, The Netherlands) and Oxysoft software (v. 3.0.103.3, Einsteinweg, The Netherlands) during the exercise testing as previously described (22). Briefly, the NIRS device was adhered to the gastrocnemius, at the approximate location where the participant felt the most pain, using a commercially available double-sided adhesive and a commercially available black bandage to prevent extraneous light from reaching the device (15, 22). NIRS data were collected continuously at a frequency of 10 Hz and used to

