estimate the change in tissue saturation (StO₂), deoxygenated hemoglobin concentration ([HHb]) and oxygenated hemoglobin concentration ([O₂Hb]) at resting baseline and during the walking test. Upon walking test completion, the participant stood in a resting standing position and a thigh rapid inflation cuff (cuff model SC10, D.E. Hokanson, Bellevue, WA) was placed on the thigh ~ 3-4 centimeters proximal to the knee on the limb with the NIRS device. The cuff was inflated to ~ 250- 260 mmHg for 5 min to deoxygenate the tissue with the same rapid inflation cuff system used for FMD (22, 25). The cuff pressure was released after 5 min, and the peak hyperemic response following cuff release was used to determine the 100% oxygenation level for each participant and was used to calculate normalized [HHb] (22, 25). The raw NIRS data were reduced to 1 Hz files and exported to Microsoft Excel files for later analysis.

Autonomic function

Autonomic nervous system function was measured using heart rate variability. Participants wore a simple heart rate monitor (Suunto Smart Sensor, Suunto, Vantaa, Finland). The researcher assisted the participant with putting on the heart rate monitor. The participant was positioned in a supine position on a padded examination table for 5 minutes. The subject was then be assisted with standing upright in front of the table for 5 minutes. Heart rate was recorded during supine and standing positions and used to determine autonomic nervous activity.

Statistical analysis

The Shapiro-Wilk test was used for all dependent variables to determine the normality of the data. Independent *t*-tests were used to determine any differences between subject characteristics at the MitoQ and PL visits. A two-way repeated measures analysis of variance³ (ANOVA) [group (MitoQ and PL) x time (before and after supplement intake)] was used to compare the changes between MitoQ and PL intake within and between groups on the dependent variables. When a significant main effect or interaction was found, paired *t*-tests were used for *post-hoc* comparisons for the normally distributed variables, and paired samples

3

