Wilcoxon tests were used for non-normally distributed variables. Based on a power calculation from a previous study, a sample size of a minimum of total 14 (n = 7 per group) would allow for 80% power to detect differences between FMD between MitoQ vs. PL (26). Associations between dependent variables were assessed using Pearson's product-moment correlation coefficient. Effect size analyses were conducted using Cohen's *d* and interpreted as 0.2 as a small effect size, 0.5 as a medium effect size, and 0.8 as a large effect size (22, 27). All analyses were performed using SPSS 26.0 (IBM, Armonk, NY). Descriptive characteristics are presented as Mean \pm SD, and all other data are presented as Mean \pm SE. Statistical significance was set to *p* < 0.05.

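### No primary outcome is named and the powered FMD is not tied to an artery, so the plan leaves open which test carries the MitoQ conclusion

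*Combined protocol and SAP*

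**What the plan says.** The Statistical analysis section gives one error rule for the whole study: "Statistical significance was set to *p* < 0.05". No adjustment for multiple outcomes and no testing order is described.

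The same two-way repeated measures ANOVA "was used to compare the changes between MitoQ and PL intake within and between groups on the dependent variables", and those variables are not enumerated or ranked. Post-hoc paired tests follow "When a significant main effect or interaction was found", so a group or time main effect is enough to open them. The section then adds correlations: "Associations between dependent variables were assessed using" Pearson's coefficient, with no pairs specified.

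The only outcome with a power basis is FMD. The sample size is said to give 80% power "to detect differences between FMD between MitoQ vs. PL". The Endothelial function section describes two FMD outcomes: "Endothelial function was assessed using brachial artery flow-mediated dilation (FMD) and popliteal artery FMD". Other sections add walking outcomes (patients were asked "to walk as long as they could tolerate even if the claudication persisted (maximal walking time and distance"), NIRS measures and heart rate variability.

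The word primary is attached to no outcome. The Participants section says "This study was registered with" a public registry, but nothing from the registration about outcomes is carried into this text.

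**The concern.** Each single test keeps its own 5% level. The difficulty is that the plan does not say which test decides whether MitoQ worked. FMD looks like the lead outcome because it alone has a power statement, yet there are two FMD outcomes. Within each outcome there are also several routes to a significant result: the interaction, a main effect followed by a comparison after intake, or a change within the MitoQ visit.

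A reader of the results could not tell a positive finding on the intended test from a positive finding on whichever test happened to cross the threshold. The chance of the latter under no effect depends on which reading is adopted, and on some readings it is well above 5%.

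**Working it through.** **Inputs from the document.** Per-test level 0.05 (sidedness not stated, taken as two-sided); 13 participants recruited; two-period crossover, so MitoQ versus placebo is a within-person comparison; two FMD arteries; post-hoc tests opened by any significant ANOVA term.

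**Assumptions.** The document gives no correlation between arteries, so 0 to 0.9 is used. Data are normal, all four cells per person are equally correlated, and the Wilcoxon branch is not modelled. For the scenarios with a time effect, the within-person correlation is 0.5, and a shift of 0.3 or 0.5 SD from before to after intake is applied equally in both arms.

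**The plan's own figure.** The stated 80% power with 14 in total cannot be reproduced, because no effect size or SD is given. Solving backwards with the noncentral t, 14 paired participants have 80% power at a standardised within-person difference of about 0.81. Seven against seven independent participants would need about 1.63.

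**Reading A: group x time at either artery counts.** In this 2x2 within-person layout the interaction test is the paired t-test (12 df) on MitoQ change minus placebo change.
- Independent arteries: 1 - (1 - 0.05)^2 = 1 - 0.9025 = 9.75%.
- Correlated arteries, normal theory, 1 - P(|Z1| < 1.96 and |Z2| < 1.96): 9.1% at correlation 0.5 and 7.0% at 0.9.
- Simulated paired t, n = 13: about 9.7% at correlation 0, 9.1% at 0.5, 7.2% at 0.9.
- One artery named in advance: 5%, whether or not there is a time effect.

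**Reading B: the plan's gate, then only the MitoQ versus placebo comparison after intake counts.** A significant group, time or interaction term is required first.
- No time effect: one artery 3.0%; two arteries 6.0%, 5.7% and 4.5% at correlation 0, 0.5 and 0.9.
- Shift of 0.5 SD in both arms: two arteries up to about 8%, because the time term opens the gate more often.

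**Reading C: the plan's gate, then either a within-MitoQ change or the post-intake comparison counts.**
- No time effect: one artery about 5%; two arteries 8.0-10.6% (correlation 0.9 to 0).
- Shift of 0.3 SD in both arms: one artery about 16%.
- Shift of 0.5 SD in both arms: one artery about 37%.

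The excess under C with a time effect comes from the post-hoc trigger, not from having two arteries: a change shared by both arms is read as a MitoQ effect. All measurements are repeated about an hour after ingestion (Design section), so a shared shift is possible. The document gives no figure for its size.

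**The case against.** The strongest reply is that the plan nowhere says significance at either artery would count as success. The registration or the study cited for the power calculation may fix both the primary outcome and the artery. This stands: the 7-10% is conditional on one reading, and if an artery was fixed beforehand its error rate on the group x time test is 5%. What does not follow is that nothing needs changing. The document presents itself as the full protocol and analysis plan, and a choice made elsewhere has to appear in it to constrain the analysis.

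A second reply is that the powered contrast is MitoQ versus placebo, and that under the plan's gated post-intake comparison the two-artery figure is close to 5%. That is right when there is no time effect. It is one reading among several, and the plan does not select it.

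A third is that FMD may not be the intended lead at all: the document's title puts leg function first. This also stands, and it is why the remedy should not impose FMD.

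Two stronger readings should be resisted. A reader might count every measured variable and infer a very large overall false-positive rate. The dependent variables are not listed and their correlations are not given, so no such total can be supported. A reader might also infer that no primary was ever chosen, or that one was chosen after seeing results. The document is silent on both.

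**Conclusion.** The point holds as a defect of specification. The document does not name a primary outcome, does not say which artery its FMD power statement covers, and lets main effects and unspecified post-hoc tests share one unadjusted threshold.

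The size depends on the reading: about 7-10% for group x time at either artery; about 4.5-6% for the gated post-intake comparison over two arteries with no time effect, rising to about 8% with a 0.5 SD shared shift; and, at a single artery, about 5% rising to 16-37% with a 0.3-0.5 SD shared shift if a within-MitoQ change counts. The correlations and shifts are assumptions. It is certain that the document omits the primary outcome and the artery. It is not established that the trial's actual error rate was inflated. The matter should be corrected, but it does not by itself invalidate any single test.

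**What to change.** In the Statistical analysis section:
- State the one primary outcome that was prespecified and when it was fixed. If it is FMD, name the artery.
- Base the MitoQ conclusion on one group x time contrast (MitoQ change minus placebo change) at two-sided 0.05, not on a main effect or a within-MitoQ change.
- List the remaining outcomes, including the second artery if FMD is primary, as secondary or exploratory, with estimates and 95% confidence intervals and no confirmatory claim. Treat the correlations the same way.
- If prior choice cannot be shown, label all outcomes exploratory. The text is in the past tense with recruitment reported, so a primary named now would have to be disclosed as post hoc.

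**Cost.** No new data are needed and the primary keeps its full 0.05. Isolated results below 0.05 on other outcomes would no longer support a claim of effect.

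The alternative of testing both arteries with Holm costs power for an effect at one artery, because the first step is at 0.025. Power falls from 80% to 69% if 80% is assumed at n = 13 (standardised difference 0.85). It falls from about 76% to 64% at n = 13 if the plan's 80% is anchored at 14 paired participants (standardised difference 0.81).
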